3 ROLES & RESPONSIBILITIES

Sponsor

The Sponsor, University Hospitals of Derby & Burton NHS Foundation Trust, take on overall responsibility for appropriate arrangements being in place to set-up, run and report the research project. The sponsor is not providing funds for this study but has taken on responsibility for ensuring finances are in place to support the research.

Host Organisation

The Host Organisation, Keele University, are providing supervisory support and access to their Health and Social Care Research Quality Management System (HSCR QMS). Keele Clinical Trials Unit, Keele University are providing support and advice for the set-up, delivery and reporting of the research.

Funder

The study is funded by National Institute for Health Research, Health Education England Integrated Clinical Academic Clinical Doctoral Fellowship Scheme (HEE/NIHR ICA Programme) reference NIHR302181.

5 LIST OF ABBREVIATIONS

AE	Adverse Event
CI	Chief Investigator
CRF	Case Report Form
CRN	Clinical Research Network
CTU	Clinical Trials Network
DCF	Data Collection Form
GCP	Good Clinical Practice
ICF	Informed Consent Form
HRA	Health Research Authority
HSCR	Health and Social Care Research
NHS	National Health Service
MDC	Minimum Data Collection
OA	Osteoarthritis
PAG	Patient Advisory Group
PI	Principal Investigator
PIS	Participant Information Sheet
PPIE	Patient Public Involvement Engagement
QA	Quality Assurance
QMS	Quality Management System
REC	Research Ethics Committee
REDCap	Research Electronic Data Capture
SAE	Serious Adverse Event
SMF*	Study Master File
SMG*	Study Management Group
SOP	Standard Operating Procedure
UHDB	University Hospitals of Derby & Burton NHS Foundation Trust

7 STUDY SUMMARY

Thumb base osteoarthritis occurs in 21-45% of the adult population over 40 and can cause severe pain and difficulty with essential everyday hand use. Guidelines recommend that those seeking care should receive education and exercises (supported self-management), and, if needed, splints. However, these guidelines are based on research reporting outcomes at three months or less, often excluding those with other hand conditions and co-morbidities. In these studies, self-management was found to provide pain relief for about half of study participants, with the remaining individuals not benefiting significantly in terms of pain at three months. Furthermore, there is no research on the patient's experience of care.

The aim of this study is to investigate, using a mixed methods approach the outcomes, prognosis, and experiences of care in patients receiving usual National Health Service (NHS) care which consists of a supported self-management programme, and to generate recommendations for optimising care for thumb base Osteoarthritis (OA). The design will be a prospective longitudinal cohort study linked with a qualitative interview (and focus group) study. Four NHS sites will recruit 150 people with symptomatic thumb base OA. The primary outcome is the AUSCAN hand pain scale, additionally baseline assessments will be carried out for measures of hand function, quality of life and known musculoskeletal prognostic factors. The study endpoint is six months. Outcome assessments will be conducted by postal/online questionnaire (as applicable) at three and six months. The qualitative and quantitative results from this study will be integrated and presented to a stakeholder group meeting, where participants will be guided to generate recommendations for future care.

Plain English Summary

Background

Thumb base osteoarthritis (OA) is common in adults 40 years and over. It affects a person's ability to work, be independent and care for others. Sufferers complain of severe pain and difficulty in completing everyday tasks. The main treatment for the condition is advice on how a person can manage their condition (self-management), reduce their pain, strengthen their hands with exercises and practical tips on tackling painful tasks, sometimes providing a hand splint for support. The treatment is provided by occupational and physiotherapists. We know that this treatment helps suffers in the short term (up to three months). But the research was done in people with few other health problems and while self-management support helps provide pain relief for most people, there are some people who don't benefit. The aim of this research is to see how pain and other hand problems change over a period of six months after the start of treatment, to understand people's experience of care, and examine why some people improve, and some do not.

Research Plan

In patients receiving treatment for thumb base OA at four NHS sites, who are willing to take part, this research will: -

1. Record changes in symptoms and quality of life at three and six months from when treatment began in a postal questionnaire/survey.
2. Discuss the experience of care and people's beliefs about what makes treatment a success by interviewing a small group of patients.
3. Analyse patient characteristics, to see if it is possible to determine how they will respond to treatment.
4. Develop recommendations for improving care.

Burden

[figure not shown]
The questionnaires required will take up to 30 minutes to complete (at three time points). The treatment given is usual NHS care for thumb base OA and will not present any additional risks.

Benefits

The study will help researchers investigate ways of improving the care of people with thumb base OA in the future.

Study Title	Outcome and Prognosis of Supported Self-management in Thumb Base Osteoarthritis: A Prospective Cohort Study.
Short Title	TOPS Study
Study Design	Observational Cohort Study with interviews and focus groups.
Trial Intervention (where applicable)	N/A
Study Participants	Adults with thumb base osteoarthritis
Planned Sample Size	150
Follow-up Duration	6 months
Planned Study Period	May 2023 – July 2025
Objectives:	Outcome Measures for Each Objective:
Determine the 6-month outcomes in a cohort of patients receiving supported self-management.	AUSCAN – pain & function EQ-5D-5L – quality of life OMERACT/OARSI Responder Criteria (AUSCAN & Global rating of change) PROMIS SFv2 4a – participation in social roles & activities PSEQ pain self-efficacy
To evaluate patient experiences with care and determine what factors patients and clinicians perceive contribute to outcome.	OA-QI – quality of care Qualitative data from interviews and focus groups
To investigate the association of prognostic factors with pain and function outcomes.	AUSCAN and OMERACT/OARSI responder criteria

Abbreviations: AUSCAN – Australian Canadian Hand Index, EQ-5D-5L - Quality of Life EuroQol 5 Dimensions 5-levels, OMERACT-OARSI Outcome Measures in Rheumatology Committee and Osteoarthritis Research Society International, PROMIS – Patient-reported outcome measurement information system, PSEQ – patient self-efficacy questionnaire, OA-QI - Osteoarthritis Quality Indicator.
	

8 STUDY FLOW CHART

FUNDED BY

NIHR | National Institute for
Health and Care Research

9 BACKGROUND AND RATIONALE

Thumb base osteoarthritis

Osteoarthritis (OA) is the most common cause of chronic joint pain and disability in older adults, and in the UK one third of those over 45 years seek treatment for the condition¹. Prevalence, incidence, and years lived with the disease is rising globally². Individuals with OA have poorer physical and mental health. There are also socio-economic impacts, health resource use and work impairment impacts³⁻⁵. As such OA poses a major public health challenge. Better ways are needed for reducing demand on healthcare and managing the more complex treatment needs of an aging population with multiple co-morbid conditions.

Hand OA is more common, and yet, less researched than OA at other joint sites such as the knee and hip⁶. Patients report that the impact of OA in the hand is underestimated by health professionals⁷. The hand is composed of multiple joints and as such hand OA is a complex model to study. The focus of this research is thumb base OA, which involves the trapeziometacarpal and scapho-trapezial joints. There is a high prevalence of radiographic thumb base OA (21% in 40-year-olds, increasing to 45% in those over 80 years)^{8, 9}. Thumb base OA sufferers typically experience tenderness, pain and difficulty with essential pinching tasks (writing, dressing, opening packets) during which the greatest load is taken through the basal thumb joint¹⁰. Patients consulted for this proposal point out that its effects therefore carry over into work, hobbies, sports, and caring roles. Thumb base OA is considered to be a more biomechanically driven phenotype of hand OA¹¹ (than nodal or erosive hand OA), and thus progression of disease is suspected to differ.

Treatment for thumb base OA

NICE Guidelines¹² recommend a stepped-care approach to treatment, with the following steps: (1) all patients should be offered education about the condition and self-management principles¹³ or supported self-management provided by a therapist; (2) if required, intra-articular steroid injections (3) if required, surgical consideration. However only 21-45% of patients seeking treatment in primary and secondary care receive supported self-management from a therapist and the treatments provided vary^{14, 15}. Supported self-management should comprise of education, task modification advice and exercise, it should be comprehensive and tailored to each patient. Opportunities to review the information, progress exercises and problem-solve with a therapist should be provided, the provision of leaflets alone is ineffective¹⁶. Hand splints are recommended by guidelines and routinely used^{13, 17}, however, recent evidence showed that splinting offered no additional improvement in pain

or function when combined with a comprehensive supported self-management programme¹⁸. A systematic review of randomised controlled trials (RCTs) of physical therapies (exercise and mobilisation techniques, splints and heat) for thumb base OA¹⁹ estimates that the therapies provide clinically worthwhile improvements in pain intensity of 3.1 [95% CI 2.5 to 3.8] on a 0-10 scale (4 weeks post intervention). Longer-term outcomes of treatments have not been investigated. Two large randomised controlled trials with broad inclusion criteria have found that while supported self-management is effective for pain relief on average at three months^{18, 20}, there are still significant proportions of patients who are classified as non-responders according to Osteoarthritis Research Society International (OARSI) responder criteria²¹. This suggests that response to treatment varies widely, and the variation may be due to the strong biomedical and biomechanical focus of current treatments.

Randomised clinical trials typically exclude participants with other hand disorders, but 15-35% of people presenting with thumb base OA or hand OA have another distinct hand condition^{22, 23}. Other studies exclude patients with anxiety and depression, which has been reported to be present in 20% of OA patients²⁴. Current guidelines are based on this evidence and therefore do not reflect a substantial proportion of patients treated in the NHS.

The experience of care

Limited qualitative research exists for hand and thumb base OA. One study exploring the perceptions of patients with hand OA in England⁷ concluded a perceived lack of help and advice regarding treatment. The authors suggested this was due to the clinical uncertainty of treatment, with a lack of high-quality trials and limited written information available. This study was conducted in 2010, and it would be important to know if more recent research evidence and guidelines reveal a change in perceptions. The study also emphasised the need to understand patient illness and treatment beliefs to facilitate the use of evidence-based approaches to care. A more recent study explored the experiences of having thumb base OA in New Zealanders²⁵ and results suggested that education and information on the disease was not readily available. Constant pain was of greatest concern, and resultant poor hand function led to reduced physical activity with significant mental and emotional impacts. A Dutch study explored patients' perceptions of prescribed splints, concluding that beliefs around the mechanism of effect influenced splint use²⁶. There is no research assessing the patient's experience of care, whether patient needs are addressed, or assessing the quality of care received.

The course and outcome of thumb base OA

OA is a common multifactorial disease that affects the whole joint and has a heterogeneous outcome²⁷. Currently, treatments provide symptom relief and there are no disease-modifying drugs or cure⁴. In

thumb base OA radiographic disease progression, visible deformity and significant loss of strength, movement, and hand function are observed compared to healthy controls^{28, 29}. However, weak associations have been reported to exist between the severity of radiographic hand OA and patient-reported measures of pain and function over time³⁰ indicating that other factors may explain variations in pain and function³¹. A systematic review conducted for this proposal ([name] et al, in preparation) has identified potential prognostic factors for symptomatic progression in hand OA. The factors can be divided into clinical signs, general health, psychological factors, and perceived symptom severity. Each factor is supported by limited evidence but can be assessed in the clinical cohort study proposed.

Patients involved in developing this proposal suggested that outcomes of treatment are influenced by patient psychology and confidence in the treating clinician. Research driven psychologically enhanced packages of care have been successful for knee OA³². An understanding of prognostic factors in relation to outcome has led to the effective use of enhanced treatments for those at risk of persistent low back pain³³. This stratified approach is endorsed by expert working groups as ideal for OA, where the disease course varies³⁴. It is important in conditions with a high prevalence (such as thumb base OA) to ensure enhanced treatment is targeted quickly at those who need it, while those with a good prognosis are not subject to unnecessary investigations and interventions³⁵.

In summary three issues exist with the supported self-management provided for thumb base OA in the NHS:

1. While providing pain relief, supported self-management and splint use is based predominantly on trials with follow up of less than three months¹⁹, which exclude those with other health and hand conditions.
2. Treatments for thumb base OA are reported to have variable outcomes, with a significant proportion of non-responders (50-67%)¹⁸.
3. Patient experiences of supported self-management in a stepped care approach have not been assessed.

This research proposes to determine the six-month outcome of current care, in a sample that represents the population treated in the NHS. It will evaluate the quality and patient experience of care, identify factors that are associated with outcomes and make recommendations to improve care of patients. If the findings of the proposed research are that the response to treatment in thumb base OA is influenced by modifiable prognostic factors, then this can lead to the development, evaluation and implementation of new enhanced interventions or more optimal pathways of care. The qualitative research within this proposal also sits well with a person-based approach to behaviour

change which suggests a first step in intervention development for behaviour change is to identify the key issues, needs and challenges that the intervention must address³⁶.

10 AIMS AND OBJECTIVES

Aim

To investigate, using a mixed methods approach, the outcomes, prognosis, & experiences of care in patients receiving a supported self-management programme.

Objectives

1. To determine the 6-month outcomes (change in pain, hand function, participation in social roles and activities, and quality of life) in a cohort of patients with thumb base OA receiving supported self-management in specialist NHS services. And to estimate the proportion of those who respond after treatment.
2. To evaluate patient experiences with care and determine what factors patients and clinicians perceive contribute to outcome (candidate prognostic factors).
3. To investigate the association of prognostic factors with pain and function outcomes.
4. To integrate qualitative and quantitative findings to generate recommendations for optimising current care.

11 STUDY DESIGN

This study is a mixed methods convergent parallel design, and is divided into three parts:

1. Prospective cohort study in people with symptomatic thumb base OA receiving a supported self-management programme to provide 3- and 6-month outcome data; and record any subsequent stepped care provided according to existing guidelines.
2. Qualitative Research: semi-structured interviews will describe the experience of care and explore patient perception of factors related to outcome, and a focus group will explore treating therapist perceptions of factors related to outcome.
3. Stakeholder and PPIE meeting to discuss and disseminate the results with patients and clinicians and to generate recommendations for improving care for patients.

Supported self-management for thumb base OA (Optimal NHS Care)

All participants will receive an occupational or physiotherapist led supported self-management programme, delivered in a community or secondary care setting. This programme was developed to provide optimal NHS care⁴⁹ and was found to be effective at reducing pain and improving hand function in thumb base OA over three months¹⁸. This programme equates to normal NHS care, having been adopted by the sites involved. The educational materials used, and a minimum number of appointments will be consistent across the study sites. The programme is described below adhering to guidance in the TIDieR checklist⁵⁰.

The goal of this programme is to teach the person with thumb base OA about the condition, how they can reduce pain, improve motion and strength, and to adapt tasks to use the hand in more healthy postures. This programme involves an hour-long initial appointment during which education is provided about: thumb base OA; diet; pain management; holistic medicine; and the principles of ergonomic task modification. Exercises are taught to improve the control, motion, and strength of the thumb. Patients are advised to continue the exercises three times a week. The exercise regime is graded, with progression through three stages incorporated into the programme. Progression to the next stage occurs when the exercises can be performed correctly in a pain free manner.

The delivery of the education incorporates behavioural approaches to encourage the use of ergonomic task modification techniques and exercises (such as discussion of the barriers and facilitators to self-management, and goals setting and signing of contracts). Adherence is supported with the use of an exercise and reflection diary (this diary will not be used for data collection).

To provide support there is a follow-up phone call appointment at an agreed time (approximately two weeks later) to encourage adherence to the self-management programme, and to provide further advice with any issues relating to the exercises and functional difficulties. Then there is a 30-minute appointment between four and six weeks after the initial appointment to review and progress exercises, to practice ergonomic task modification and discuss issues. This appointment (and any others deemed necessary) will be conducted face to face or remotely according to patient and clinician requirements.

According to findings of the OTTER trial¹⁸ and in line with guidance from NICE¹², splints to support the thumb base will not be provided routinely, but as required as part of a shared decision-making approach¹³ for example if a participant does not improve with the supported the self-management programme alone¹². The splints used will be chosen and fitted at the discretion of the treating therapist, providing informed choice for the patient on the options available. This splint prescription process will be according to normal clinical practice, to meet the needs of that participant. The evidence suggests there is no difference in efficacy between different splints, and that splints can have a longer-term benefit on pain⁵¹. Patients will be advised on their use according to the usual clinical practice. This is a pragmatic choice as the cohort needs to reflect optimal best practice which means: the splint will need to be the best fit; the most appropriate to use with aggravating functional tasks; provide the right level of comfort, positioning, and support according to symptom severity and the condition of the local joints and soft tissues.

There are no validated measures of adherence to therapy programmes, and Patient Public Involvement Engagement (PPIE) work for this study and the research teams experience from other studies, did not support the use of diaries for assessing adherence. So, participants and therapists will self-report on perceived adherence to the programme using a published assessment⁵², this assessment allows participants the options to report not adhering and partially or completely adhering to different elements of the programme, and was seen by PPIE representatives as being most likely to elicit a true response.

Care for other co-existing hand conditions

There will be no alterations to usual care for co-existing hand conditions (such as OA wrist or hand, carpal tunnel syndrome, trigger digits or De Quervain's disease). Data will be collected on the provision of splints, the number of appointments attended and the presence of co-existing hand conditions. A self-report questionnaire will capture whether a patient has purchased their own splint, or sought other treatments, or had a steroid injection for their thumb base OA or a co-existing condition or been placed on a surgical waiting list or had surgery.

Study Training

All collaborating therapists will be trained in standard protocols for the study. This training will include screening and study procedures; the consent process; study monitoring and data collection forms; the measures to encourage adherence; and communication with the chief investigator and the trial co-ordinator. The training will be conducted by the chief investigator. The principal investigator at each site will be responsible for ensuring the local therapists delivering care have the clinical skills required to assess and treat the participants. Additionally, as the baseline questionnaire asks about mood the principal investigator will be responsible for having a procedure in place, as per normal clinical practice, to provide appropriate sign posting or support to a participant who reports they are struggling with their mental health.

12 STUDY SETTING

Participants will be recruited from new and waiting list referrals to occupational therapy or physiotherapy departments in rheumatology, hand surgery or hand specialist community services at four NHS recruitment sites.

Eligibility criteria

This study will recruit participants with a clinical diagnosis (signs and symptoms) of thumb base OA. Radiographs are not required to diagnose and provide therapy treatment for thumb base OA, clinical assessment alone will be used¹². Ensuring there is at least one positive clinical sign of thumb base OA, will enable the assessing clinicians to confirm the diagnosis on the referral, and exclude other sources of radial sided wrist pain^{37, 38}. This diagnosis, or confirmation of diagnosis, is part of normal clinical assessment that occurs prior to providing treatment for this condition.

Inclusion criteria

- Aged 30 years and over.
- Symptomatic thumb base OA, confirmed with at least one of the following clinical signs:
 - Hard tissue enlargement of the thumb carpometacarpal joint
 - Squaring at the base of the thumb
 - Crepitus on movement of the thumb carpometacarpal joint
 - Positive adduction provocation test
 - Positive extension provocation test
 - Positive pressure shear test
 - Pain on palpation of the dorso-radial aspect of the thumb carpometacarpal joint

FUNDED BY

NIHR | National Institute for
Health and Care Research

- Able to give written informed consent.
- Available to attend Occupational Therapy/Physiotherapy/Hand Therapy sessions.

Where there is bilateral thumb OA, the most symptomatic thumb (according to the participant, considering the preceding month) will be chosen for data collection.

Exclusion criteria

- Currently receiving therapy care for thumb base OA.
- Fractures or significant injury or surgery to the wrist or hand on the included side in the previous 6 months.
- Previous surgery to the basal thumb joint on the included side.
- Red flags i.e., diagnosed rheumatic condition (gout, rheumatoid arthritis), progressive neurological signs, any acutely swollen hand joint, serious illness, or disease.
- Participants of any drug or medical device trial in the last 12 weeks.
- Recent steroid injection in their included basal thumb joint (2 months prior to baseline appointment).

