Table 1 Assessments at each study time point

Assessments	Baseline	3 months	6 months	Measurement method
AUSCAN	x	x	x	Participant self-report
Pain NRS	x	x	x	Participant self-report
Pain Frequency	x	x	x	Participant self-report

FUNDED BY

NIHR | National Institute for
Health and Care Research

EQ-5D-5L	x	x	x	Participant self-report
OA-QI	x	x	x	Participant self-report
PROMIS SFv2 4a Participation	x	x	x	Participant self-report
PSEQ	x	x	x	Participant self-report
B-IPQ	x			Participant self-report
Grip strength	x			Clinician assessment
Number of painful joints	x			Clinician assessment
Confirmation of thumb OA & presence of co-existing hand conditions	x			Clinician report
Availability of radiographs	x			Clinician report
Demographic: DOB, sex assigned at birth, ethnicity, language*, work status, income, educational level, postcode, hand dominance.	x			Participant self-report
Health: age at onset of thumb pain, duration of OA thumb, side affected, previous therapy treatment, co-morbidities, BMI*, use of NSAIDs	x			Participant self-report
START psych subscale	x			Participant self-report
GROC		x	x	Participant self-report
Therapy adherence questionnaire		x	x	Clinician and Participant self-report
Number of therapy appointments attended		x		Clinician report
Information regarding additional treatments provided as part of stepped care.		x	x	Clinician and Participant self-report

Key: NRS - numerical rating scale, EQ-5D-5L - EuroQol 5 Dimensions 5 Levels Questionnaire health status and quality of life, OA-QI - Osteoarthritis (care) Quality Indicator, PROMIS SFv2 - Patient-Reported Outcomes Measurement Information System Short Form for participation in social roles and activities, PSEQ - pain self-efficacy questionnaire, DOB - date of birth, BMI - body mass

FUNDED BY

NIHR | National Institute for
Health and Care Research

index, NSAIDS – non steroidal anti-inflammatory medication, GROC – global rating of change question, B-IPQ – Brief Illness perception questionnaire.

*BMI, participants first language and whether an interpreter is needed, are self-report collected in clinician DCF (not baseline questionnaire).

Table 2: Details of (Potential) Prognostic Factor Assessments

Concept	Measurement method	Detail
Perceived symptom severity		
Hand Pain	Australian Canadian Hand Index (AUSCAN) Participant self-report	Pain subscale – 5 items about the severity of pain at rest and with function in the last 48 hours.

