15 STATISTICS AND DATA ANALYSIS

Quantitative analysis

Summary of baseline data and flow of patients

The full statistical analysis plan will be written, and agreed prior to analysis, hence only an outline of the analysis is described below. The presentation of data and reporting will be informed by the Strobe statement⁶⁶. The numbers of those examined for eligibility and those included and those completing follow up will be presented with a flow chart. The reasons for non-participation or withdrawal will be presented. Key socio-demographic and health data will be presented and compared between those who do and do not complete the three and six-month follow up. Descriptive statistics will be used for this analysis (frequencies and percentages for categorical data, means and standard deviations for numerical data).

Outcome analysis – descriptive statistics

Descriptive statistics, including 95% confidence intervals where relevant, will be used to estimate:

- Overall outcomes of care at three and six months - the change from baseline in pain, function, participation, pain self-efficacy and health related quality of life; and the proportions classed as responders at each time point.
- The proportions who required additional treatments and what care was provided will be described.
- Summarised scores for perceived quality of care (OA-QI).

Outcome analysis

Linear regression for continuous outcomes will be used to explore the association of selected prognostic factors with outcome (pain and function); logistic regression for binary outcome (OMERACT-OARSI responders). Crude (unadjusted) estimates will be calculated as well as estimates of the strength of associations adjusted for relevant covariates (e.g., age, gender, socioeconomic status, presence of comorbidities, baseline value of the outcome). Results from the interview study will inform the order of prognostic factors to be included in the analysis of the relationship between candidate prognostic factors and outcomes. Model fit will be explored using statistics such as R-squared or C-statistic to estimate predictive value, i.e., how well the prognostic factor can explain variability in outcome over and above demographic variables and baseline pain/function.

Sample size calculation

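### Surgery or an injection arranged before entry is not recorded at baseline, so it may not be separable from stepped care that follows the programme

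*Protocol*

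**What the plan says.** Section 12 of the protocol recruits from therapy "departments in rheumatology, hand surgery or hand specialist community services at four NHS recruitment sites". Three of its exclusions concern earlier or current treatment of the thumb base: "Previous surgery to the basal thumb joint on the included side", "Currently receiving therapy care for thumb base OA", and a steroid injection to that joint within 2 months before baseline. (Recent wrist or hand surgery in general is excluded separately.) The section on patient and public involvement (section 18) explains that people who have had treatment before are included on purpose.

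At baseline, Table 1 (section 14) asks about previous therapy treatment and NSAID use. The row "Information regarding additional treatments provided as part of stepped care" is marked at 3 and 6 months only, with clinician and participant as sources. Section 11 describes a self-report questionnaire covering a self-bought splint, other treatments, a steroid injection, and whether the patient has "been placed on a surgical waiting list or had surgery". It also says that data on splint provision will be collected. It states no recall period.

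Treatment beyond the programme is a secondary outcome in section 13, and the design in section 11 speaks of stepped care that comes after the programme. Section 15 gives the summary: "The proportions who required additional treatments and what care was provided will be described".

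**The concern.** To say that treatment was subsequent, or that a patient required it, one must know the state at entry. The schedule does not collect that state for a surgical listing, a booked injection or a splint in use. Recruitment through hand surgery services makes such arrangements plausible, and section 14 notes that the wait between referral and treatment varies.

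At stake is the descriptive account of the care pathway. Section 9 says patients' experience of stepped care has not been assessed, objective 4 is to generate recommendations for care, and section 19 plans to report treatment delivered over 6 months in the main results paper. If care already in train is mixed with care that followed the programme, the programme will seem to leave more people needing a further step than it does.

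**Working it through.** **Setting the sections side by side**

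| Status at entry | Excluded by section 12? | Baseline item in Table 1? | Asked about at follow-up (section 11)? |
|---|---|---|---|
| On a surgical waiting list | No; only completed basal thumb surgery is | None | Yes, listing and surgery |
| Injection booked | No; only one already given within 2 months is | None | Yes, once given |
| Splint in use | Not as such; only current therapy care is | None directly; earlier therapy may capture some therapist-supplied splints | Yes, self-bought; provision also collected |

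The first two rows are clear gaps. The third is partial: what remains uncaptured is current use and self-bought splints.

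**Would a question limited to the period since baseline be enough?** Not fully. It would separate an old listing from a new one. But a patient listed or booked before entry who then has the operation or injection during follow-up would truthfully answer yes. Only status at entry, or the date of listing or booking, separates that patient from one referred on after the programme.

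**Size**

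The protocol gives no prevalence of pre-arranged treatment and no expected step-up rate, so there is no planned figure to reproduce and what follows is an illustration. Inputs:

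- N = 150 recruited with 30% loss (section 15), so 150 × 0.70 = 105 expected at 6 months.
- q = share entering with treatment already arranged. Assumed 5% to 15%.
- r = proportion of the rest who newly need treatment. Assumed 15%.
- All pre-arranged treatment is reported at follow-up and none is separated out. Assumed.

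Observed proportion = q + (1 − q) × r.

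- q = 5%: 0.05 + 0.95 × 0.15 = 0.1925, that is 19.3%. Ratio to r: 0.1925 / 0.15 = 1.28.
- q = 15%: 0.15 + 0.85 × 0.15 = 0.2775, that is 27.8%. Ratio: 0.2775 / 0.15 = 1.85.
- People entering with arrangements, among 105: 0.05 × 105 = 5.25 and 0.15 × 105 = 15.75, so about 5 to 16.

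Sensitivity to r:

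- With r = 20%, q = 2%, 5% and 10% give 21.6%, 24.0% and 28.0%.
- Across r = 10% to 30%, the excess over r is 3.5 to 4.5 percentage points at q = 5%, and 7 to 9 points at q = 10%.

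**The case against.** The strongest reply is that the follow-up forms are not shown. They may ask for dates or limit the question to the period since baseline, and the wording in sections 11 and 13 points towards treatment that comes after the programme. The Table 1 row also has a clinician source, and a clinician who knows the history could tell old arrangements from new. This stands in part. A reader might infer that pre-arranged treatment definitely will be counted as stepped care; the documents do not support that. They show only that the schedule has no stated means of telling the two apart.

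A reader might also infer that the information is lost for good. Section 16 allows data to be drawn from therapy records, and section 14 has a routine medical history taken at the screening visit, so partial recovery is possible. Nothing says, however, that the history is transcribed as study data for these items.

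Third, the definition of required treatment and its denominator are ordinary content for the statistical analysis plan. That is fair, and their absence is not the point here. The assessment schedule is protocol content, and no analysis plan can use a baseline status that was not collected.

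Fourth, nothing shows that many patients arrive already listed. Section 9 places supported self-management before injection and surgery, and section 14 recruits people referred for initial therapy. This stands, and it is why the size stays an assumption. Simply adding the two shares (15% + 5% = 20%; 15% + 15% = 30%) suggests up to a doubling, but that compares different denominators. If 15% of all entrants are new cases, the rates among those at risk are 15/95 = 15.8% and 15/85 = 17.6%, so the ratios are 1.27 and 1.70.

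**Conclusion.** The gap is real and limited. Patients listed for surgery or booked for an injection can enter, no baseline item identifies them, and the same treatments are collected later and summarised as required. The proportion needing further treatment may therefore be overstated. On the assumed inputs (5-15% with arrangements at entry, 15% newly needing treatment among the rest, everything reported and nothing separated) it would read about 19-28% instead of 15%. The true size is unknown and could be small. The splint part is weaker than the surgery and injection parts.

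A reader might take this as a fault in the eligibility criteria or in the main results. It is neither: broad inclusion is deliberate, and AUSCAN measurement and the sample size are unaffected. It directly affects one descriptive secondary outcome, at low to moderate severity. It is best treated as a cheap improvement.

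**What to change.** Leave eligibility unchanged. Add three items for the included thumb to the baseline clinician form: on a surgical waiting list, injection already booked, splint in current use. Report treatment arranged before baseline separately from treatment newly arranged afterwards, and give the step-up proportion for each treatment among those who did not already have that status. For participants already enrolled, take the status from therapy records where available, and state for how many it could not be established.

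The cost is a few extra baseline items and a record look-up that may be incomplete. The reported step-up proportion will be lower and slightly less precise because its denominator is smaller.
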